9.4.3 Analysis of Secondary Endpoints

Response rates will be summarized and presented with 95% exact binomial confidence intervals. The comparison of response rates will use Fisher's exact test.

Kaplan-Meier methods will be used to summarize time-to-event outcomes including the primary endpoint (median TTP) and secondary endpoints (PFS, TTF, OS). Proportions of patients with TTP, PFS, and TTF equal to or exceeding 6 months will be calculated with 95% confidence intervals. Tumor response by RECIST 1.1 measurements will be presented descriptively for the study cohort.

- **AFP Response:** Baseline levels (high or low) will be compared to absolute TTP to determine if there is an association using Fisher's Exact tests or by Wilcoxon Rank-Sum test. Changes in levels on therapy with temsirolimus and sorafenib will be measured as an increase by $\geq 50\%$ from baseline, stable value within 50% of baseline, or decrease by $\geq 50\%$ from baseline. The change in level will be used to evaluate the predictive value for TTP. Fisher's Exact tests will be used to test for significance. Kaplan-Meier methods and Log-rank tests will also be used to estimate TTP based on the AFP.

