9.1.2 Primary Endpoint

Median TTP will be calculated in months from date of first dose of protocol therapy to date of removal from study for radiographic (per RECIST 1.1) and/or clinical progression including death attributed to progression. For patients removed from study for other reasons than progression (such as toxicity, withdrawal of consent, or death from other causes than documented radiographic and/or clinical progression), TTP will be censored at the date last known to be progression-free.

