9.2 Determination of Sample Size and Accrual Rate

9.2.1 Sample Size and Power Estimate

The sample size for this phase II study will be 25 patients under the assumption that the time to progression is approximately exponentially distributed and patients come onto study uniformly

during the study accrual. A sample size of 25 evaluable patients will have sufficient power to detect the difference between the null hypothesis that the median TTP is less than 3 months (based on historical controls) and the alternative hypothesis that the median TTP is more than 6 months. The study will have a 1-sided significance level of 10% and a power of 88% under the exact test for comparison of the TTP rates between $p_0 < 25\%$ versus $p_1 > 50\%$ at 6 months.

A median TTP of > 6 months would constitute a meaningful outcome in advanced HCC, based upon the benchmarks of first-line TTP of 5.5 months in the SHARP study and 2.8 months in the Asia-Pacific study.(Llovet, Ricci et al. 2008; Cheng, Kang et al. 2009) If median TTP is > 6 months in this study, a randomized phase II trial to compare the combination therapy to single-agent sorafenib should be considered. Such a trial would be much larger and more costly, however, and should not be undertaken prior to the current study to confirm that there is tolerability and a signal of efficacy to warrant proceeding with the larger trial, noting in particular the challenges to accrual in first-line HCC studies historically, as faced by contemporary cooperative group studies CALGB 80802 and ECOG 1208.

Accrual of 25 paired archival tumor and blood specimens also constitutes a meaningful endpoint in that it will enable future biomarker studies in subsets of patients with radiographic response, AFP response, prolonged stable disease, and primary progression, including potential exploratory studies for association with tissue biomarkers of mTOR pathway activation (such as pS6 staining).(Villanueva, Chiang et al. 2008)

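### Section 9.4.3 tests AFP against TTP with Wilcoxon and Fisher tests that have no rule for censored times, and does not say that the log-rank test governs

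*Combined protocol and SAP*

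**What the plan says.** The AFP paragraph of Section 9.4.3 contains three analyses of AFP against TTP.

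- Baseline AFP: "Baseline levels (high or low) will be compared to absolute TTP to determine if there is an association". The method is given in the words "to determine if there is an association using Fisher's Exact tests or by Wilcoxon Rank-Sum test".
- Change in AFP, in three classes (a rise of at least 50%, a fall of at least 50%, or in between), is assessed as a predictor of TTP. Fisher's exact test is named for significance.
- Finally: "Kaplan-Meier methods and Log-rank tests will also be used to estimate TTP based on the AFP".

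The outcome is a censored time. For patients removed for toxicity, withdrawal of consent or death from other causes, Section 9.1.2 states that "TTP will be censored at the date last known to be progression-free". Section 2.4.1 agrees. Section 7.1.2 gives a different censoring date but also censors these patients.

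The plan does not define absolute TTP for a censored patient, the cut that turns TTP into a Fisher table for AFP, the boundary between high and low baseline AFP, the significance level of these tests, or which result is the one to report.

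**The concern.** Wilcoxon rank-sum and Fisher's exact tests need a known value for each patient. Used on raw times, Wilcoxon ranks a patient removed for toxicity at month 1 level with one who progressed at month 1. A Fisher table must place a patient censored before the cut in one column or the other. If patients in one AFP group leave early without progression more often, the test can then show a TTP difference that is only a dropout difference.

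Such removals are to be expected. Sections 5.2 and 5.3 take a patient off study when either drug is stopped, and Section 5.3 generally does so when a toxicity hold exceeds 28 days.

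The paragraph therefore puts tests that ignore censoring beside one that handles it, for the same question, with no order of precedence. Section 9.4.4 relates tissue markers to TTP by Cox regression, so the plan already handles this outcome properly elsewhere. What is at stake is the credibility of a named secondary objective.

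**Working it through.** **The plan's own figure.** The documents state no error rate for the AFP tests. The only design figure is for the primary endpoint: "The study will have a 1-sided significance level of 10% and a power of 88% under the exact test". It reproduces. With 25 patients and 6-month rates of 25% v 50%, requiring at least 10 successes gives an exact alpha of 0.071 and a power of 0.885. From it I take only N = 25 and the two medians, 3 and 6 months.

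**Inputs assumed, because the documents are silent.**
- Two-sided 5% level.
- Two splits of 25 patients: near-equal (13 v 12), and 19 v 6. The second follows from Section 1.2.3.1, where 16 of 21 phase I patients (76%) had AFP of at least 20 ng/mL, and 0.76 × 25 = 19. That threshold is not stated to be the high/low boundary.
- Dropout without progression: a share f in each AFP group, varied from 0% to 70%.

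**Why equal dropout is harmless and unequal dropout is not.** Give both groups the same exponential TTP with hazard λ = ln 2 / median. Independent exponential dropout with hazard λf/(1−f) removes a share f before progression. The observed time then has hazard λ/(1−f). The chance that a patient from group A has a longer observed time than one from group B is

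P = (1−f_A) / [(1−f_A) + (1−f_B)].

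Equal dropout gives 0.5, the null value. For 10% v 30%, P = 0.9/1.6 = 0.5625. For 10% v 50%, P = 0.9/1.4 = 0.643.

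The null standard deviation of the Wilcoxon estimate of P is √[(n₁+n₂+1)/(12n₁n₂)]:
- 13 v 12: √(26/1872) = 0.118
- 19 v 6: √(26/1368) = 0.138

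With z = (P−0.5)/SD, the rejection rate is about Φ(z−1.96) + Φ(−z−1.96):
- 13 v 12, 10% v 30%: z = 0.53, rate 8.3%
- 13 v 12, 10% v 50%: z = 1.21, rate 22.8%
- 19 v 6, 10% v 50%: z = 1.04, rate 17.9%

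**Simulation.** Two sets were run with no true association. One had 6,000 trials per setting and median TTP 5 months. The other had 3,000 trials per setting, medians 3 and 6 months, uniform accrual over 24 months and a data cut at 30 months (Sections 3.7.1 and 3.7.2). The Monte Carlo standard error with 3,000 trials is √(0.05×0.95/3000) = 0.4 points near 5%, and 0.7 points near 21%.

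| Dropout by AFP group | Split | Wilcoxon on raw times | Log-rank |
|---|---|---|---|
| Equal (0%, 25% or 50% in both) | both | 4.2–6.6% | 5.6–7.7% |
| 10% v 30% | near-equal | 7.2–7.9% | 5.7–6.2% |
| 20% v 50% | near-equal | 14.8% | 5.0% |
| 10% v 50% | near-equal | 21.0–22.3% | 5.1–5.7% |
| 10% v 50% | 19 v 6 | 14.5–19.6% | 6.2–7.1% |

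Over all settings log-rank ran from 4.9% to 7.7%. Its highest values (7.5–7.7%) came with no dropout at all, so they reflect the small sample and not the censoring.

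**Fisher.** The cut is unstated. Taking 6 months, and counting a patient censored before then as not reaching it, the error was 4% or less with equal dropout and 0.2–18.7% at 10% v 50%. It passed 20% only at about 0% v 50% or wider.

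**The case against.** The strongest reply is that the large figures come from an assumption and not from the plan. The documents give no dropout rate by AFP group and no reason to expect a fivefold difference. At 10% v 30% the excess error is two to three points. With 19 v 6, the only split the documents suggest, even 10% v 50% stays below 20%. All of this stands.

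A reader might infer that censoring by itself pushes the error above 20%, or that Fisher's test shares that figure. The documents and the check support neither. Equal censoring leaves Wilcoxon near 5%, and Fisher is often conservative.

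It can also be said that log-rank is already planned, that absolute TTP is undefined so that ranking raw times is only one reading, and that some withdrawals never reach the test because Sections 3.2 and 9.4.1 replace patients found ineligible. The last point is limited: Section 3.2 does not replace eligible patients who have received a dose, and toxicity removals and deaths from other causes remain censored. The first two describe the gap without closing it, since no passage says how censored times are handled or which test counts.

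Log-rank is not perfect either. The simulated dropout was unrelated to progression within each AFP group. Removal for toxicity may not be.

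**Conclusion.** The concern holds as a mismatch between test and endpoint. Wilcoxon and Fisher tests are named for a censored time with no handling rule, and a suitable test stands beside them without precedence. That conclusion does not depend on any dropout figure.

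The size does. If censored times are used as observed times at a two-sided 5% level, Wilcoxon is near nominal with equal dropout, about 7–8% at 10% v 30%, and about 21–23% at 10% v 50% in near-equal groups (about 15–20% with 19 v 6). Log-rank is about 5–8%. The dropout rates, level and splits are assumptions. No single error rate can be given for Fisher until its cut and coding are stated.

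A reader might also infer that the trial's go/no-go decision is at risk. It is not: this is a secondary association analysis, and that decision rests on the overall TTP result (Sections 1.3 and 9.2.1).

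**What to change.** In Section 9.4.3, delete the Wilcoxon and Fisher tests of baseline AFP against TTP and the Fisher test of AFP change against TTP. Make log-rank, with a Cox hazard ratio and 95% confidence interval, the single AFP–TTP analysis, and state the boundary between high and low AFP.

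For AFP change, classify patients at a fixed early visit and analyse TTP from that visit among those still at risk (a landmark analysis), or enter AFP as a time-dependent covariate. Section 9.4.4 already uses AFP at Cycle 2 Day 1, which could serve as the landmark. This is needed because Section 9.1.3 measures AFP response at its best value, and patients followed longer have more chances to reach a good one.

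Fisher's exact test may be used for AFP against best response, which is not a censored time. Section 9.4.3 does not currently specify a test for that association.

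The cost is a few sentences in the analysis plan. Log-rank and Cox are already in it, AFP is already drawn on Day 1 of every cycle, and no data collection changes.

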2.4 Endpoints

2.4.1 Primary Endpoint

- Median TTP will be calculated in months from date of first dose of protocol therapy to date of removal from study for progression. For patients removed from study for other reasons than progression (such as toxicity, withdrawal of consent, death without documented progression, or other reasons without clinical or radiographic evidence of tumor progression), TTP will be censored at the date last known to be progression-free.

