2.4.2 Secondary Endpoints

- Response rate (RR) will be measured by RECIST version 1.1.
- Median PFS will be calculated in months from date of first dose of protocol therapy to date of documented disease progression or death from any cause. For patients removed from study for other reasons than progression or death, PFS will be censored at the date last known to be progression-free.
- Median OS for all enrolled patients who receive at least one dose of protocol therapy will be calculated from date of first dose of protocol therapy until date of death, using chart review and/or follow up phone calls to determine date of death in patients after removal from study.
- TTF will be measured from date of first dose of protocol therapy to date of study discontinuation for progression, death, or adverse events (related or unrelated). For patients removed from study for other reasons (such as noncompliance or withdrawal of consent), TTF will be censored at the date of study discontinuation.
- In patients with baseline AFP ≥ 20 ng/mL, AFP response will be measured by the percent change from baseline value to the value at the time of best AFP response. The proportion

of $\geq 50\%$ decline from baseline will be measured. The change in AFP will also be examined for association with absolute TTP and best response.

- Toxicity will be measured using Common Terminology Criteria for Adverse Events (CTCAE) version 4.0. The frequency of dose reduction, treatment delays, and discontinuation for lack of tolerability will be quantified.

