3.7.2 Study Completion

The study is expected to reach completion once the final patient has been enrolled and all patients have had potential for at least 6 months of follow up or been removed from study. Study completion is expected approximately 2.5 years from study opening.

4. Study Drugs

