6.1.2 Treatment Period

6.1.2.1 Study Procedures – Cycle 1

Days 1, 8, 15, and 22 (within 7 days)

- Complete physical examination, including height and weight measurement
- Vital signs, including temperature, blood pressure, heart rate, pain score, and oxygen saturation
- Evaluation of clinical response or deterioration
- Evaluation of adverse events
- Concomitant medications

- Safety laboratory assessments: CBC w/ Diff, complete metabolic panel (electrolytes, BUN, creatinine, glucose, calcium, magnesium, phosphorus, total bilirubin, direct bilirubin, alkaline phosphatase, albumin, AST, and ALT), INR
- Serum AFP tumor marker (Day 1 only)
- Blood specimen collection for CTC testing (Day 1 only)
- Banking of blood specimens for possible future correlative studies (Day 1 and 8 only) (See Study Laboratory and Procedures Manual)

6.1.2.2 Study Procedures – Day 1 of Cycles 2 and beyond (within 7 days)

- Complete physical examination, including height and weight measurement
- Vital signs, including temperature, blood pressure, heart rate, pain score, and oxygen saturation
- Evaluation of clinical response or deterioration
- Evaluation of adverse events
- Concomitant medications
- ECOG Performance Status
- Safety laboratory assessments: CBC w/ Diff, complete metabolic panel (electrolytes, BUN, creatinine, glucose, calcium, magnesium, phosphorus, total bilirubin, direct bilirubin, alkaline phosphatase, albumin, AST, and ALT), INR
- Fasting total cholesterol, triglycerides, and blood glucose (odd cycles only)
- Hepatitis B viral DNA quantitative in patients with positive hepatitis B viral load at baseline and/or positive HBsAg, HBcAb total, and/or HBcAb IgM (odd cycles only or more frequently at investigator's discretion).
- Imaging with CT chest (with or without contrast) plus triphasic CT abdomen and pelvis with intravenous contrast or triphasic gadolinium-enhanced MRI abdomen/pelvis to assess sites of known tumor using RECIST 1.1 measurements and to monitor for lung toxicity (odd cycles only, every 8 weeks \pm 7 days, starting Cycle 3, Day 1)

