9.1.3 Secondary Endpoints

1. Response rate (RR) will be measured by RECIST version 1.1.

2. Median PFS will be calculated in months from date of first dose of protocol therapy to date of study removal for documented radiographic and/or clinical disease progression or death from any cause. For patients removed from study for other reasons than progression or death, PFS will be censored at the date last known to be progression-free.
3. Median OS for all enrolled patients who receive at least one dose of protocol therapy will be calculated from date of first dose of protocol therapy until date of death, using chart review and/or follow up phone calls to determine date of death in patients after removal from study. The survival of patients still alive after 5 years of follow up post study discontinuation will be censored.
4. TTF will be measured from date of first dose of protocol therapy to date of removal from study for progression, death, or toxicity. For patients removed from study for other reasons (such as noncompliance or withdrawal of consent), TTF will be censored at the date of study discontinuation.
5. In patients with baseline AFP ≥ 20 ng/mL, AFP response will be measured by the percent change from baseline value to the value at the time of best AFP response. The proportion of $\geq 50\%$ decline from baseline will be measured. The change in AFP will also be examined for association with absolute TTP and best response.
6. Toxicity will be measured using Common Terminology Criteria for Adverse Events (CTCAE) version 4.0. The frequency of dose reduction, treatment delays, and discontinuation for lack of tolerability will be quantified.

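### Section 9.4.3 compares TTP by on-therapy AFP change with no visit fixed, so time on study helps decide the AFP class and can produce false associations

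*Combined protocol and SAP*

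**What the plan says.** - **Definition.** Section 2.4.2 says that, in patients with baseline AFP of at least 20 ng/mL, "AFP response will be measured by the percent change from baseline value to the value at the time of best AFP response". Section 9.1.3 repeats this and adds: "The change in AFP will also be examined for association with absolute TTP and best response".
- **Classes.** Section 9.4.3 says: "Changes in levels on therapy with temsirolimus and sorafenib will be measured as an increase by" 50% or more, a value within 50% of baseline, or a fall of 50% or more. No visit is attached.
- **Use.** The same bullet continues: "The change in level will be used to evaluate the predictive value for TTP". Fisher's exact test is named for significance, and "Kaplan-Meier methods and Log-rank tests will also be used to estimate TTP based on the AFP".
- **Outcome.** TTP starts at first dose (2.4.1, 7.1.2, 9.1.2). For patients who leave for reasons other than progression, "TTP will be censored at the date last known to be progression-free" (2.4.1).
- **Schedule.** AFP is drawn on Day 1 of Cycle 1 and of every later 28-day cycle (6.1.2, Table 5.1). Imaging is every 8 weeks, "starting Cycle 3, Day 1" (6.1.2). At end of treatment, AFP is needed only if none was done in the preceding 4 weeks (6.1.4).
- **Elsewhere.** Section 9.4.4 fixes AFP decline at C2D1, but only for the tissue-marker tests, and fixes change in circulating tumor cells after 1 and 2 cycles. No section plans a landmark or a time-dependent covariate for AFP against TTP.

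**The concern.** The group a patient falls into is learned during the same period over which TTP is counted. A patient who progresses early has few AFP readings; one who stays on study has many. Class membership therefore depends partly on the outcome being compared, even when AFP carries no information about progression.

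The association of AFP change with TTP is a named secondary objective (2.2), and section 1.4.1 asks for AFP change to be studied as a possible predictive marker. The risk is that a pattern produced only by time on study is reported as predictive value.

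The baseline-AFP comparison in the same bullet is not affected, because that grouping is known at first dose.

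**Working it through.** **The plan's own figures.** The documents give no power or error figure for the AFP–TTP comparison. The primary design figure does reproduce: with N = 25 and 25% versus 50% at 6 months, success at 10 or more patients has exact one-sided alpha 0.071 and power 0.885, against 10% and 88% stated (9.2.1). This supports using the exponential model and medians of 3 and 6 months below.

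**Mechanism by hand.** Assume a 10% chance per cycle of a first AFP response, unrelated to progression.
- On study 3 months: 91.3/28 = 3.26, so 3 readings; chance of being a responder 1 − 0.9³ = 27%.
- On study 6 months: 182.6/28 = 6.52, so 6 readings; 1 − 0.9⁶ = 47%.

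The longer stayer is more often a responder although AFP and TTP are independent here.

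**Inputs to the simulation.**
- n = 19: in phase I, 16 of 21 (76%) had AFP of at least 20 ng/mL (1.2.3.1); 0.76 × 25 = 19.
- TTP exponential with rate ln 2/median, median 3 or 6 months (9.2.1), dated at the next 56-day scan.
- Administrative censoring uniform over 6–30 months: 24 months of accrual (3.7.1), then until "all patients have had potential for at least 6 months of follow up or been removed from study" (3.7.2).
- Assumed: 5% or 10% monthly dropout without progression; AFP independent of TTP; patients with no post-baseline AFP left out; two-sided 5% log-rank test, since no alpha is stated for this comparison.

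**Result A: the three classes of 9.4.3.** Log AFP follows a random walk without drift, SD 0.2–0.7 per cycle, 1,500 trials per setting. False-positive rates:

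| Value used | Log-rank false positives |
|---|---|
| Best | 4–19% |
| Last | 5–12% |
| First 50% change | 14–41% |
| C2D1 value | 1–8% |

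Direction was recorded in further runs at 5% dropout.
- Best value: the decrease class had the longer TTP in 78–91% of rejections in one run and 83–100% in another. The lowest reading can only fall as visits are added.
- Last value: decrease class 33–61%, increase class 37–64%.
- First 50% change: decrease 33–50%, increase 50–67%. On the log scale a 50% rise is ln 1.5 = 0.41 away and a 50% fall is ln 0.5 = −0.69, so the rise is nearer.

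**Result B: ever versus never a responder, the grouping closest to the best-value definition in 2.4.2.** 3,000 trials per setting; false positives by chance of response per cycle:

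| Median TTP, dropout | 5% | 10% | 15% | 20% |
|---|---|---|---|---|
| 3 months, 5% | 16% | 24% | 33% | 37% |
| 3 months, 10% | 10% | 17% | 23% | 27% |
| 6 months, 5% | 15% | 30% | 38% | 42% |
| 6 months, 10% | 9% | 17% | 24% | 28% |

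- At least 93% of these false positives favour responders.
- All responses by C2D1, or split over C2D1 and Cycle 3 Day 1 (C3D1): 5–6%.
- Mixed (30% at C2D1, then 10% per cycle; 2,000 trials): 12–23%.
- Fisher's test on TTP of at least 6 months: 5–21% gradual, 1–2% early.

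**Sensitivity to the model.** With continuous progression, no dropout, censoring at 18 months, and early progressors counted as non-responders, the log-rank figures are 45–67% for gradual response and 9–14% when all responses occur at C2D1. Leaving out patients with no on-therapy AFP brings the latter to about 7%.

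**After the fix.** For the responder split, a C2D1 or C3D1 landmark gives 2–6%, or 3–9% if 30% of progressions are clinical and fall between scans. A time-dependent Cox score test gives 4–7%.

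**The case against.** The strongest case against has four parts.

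- **Direction.** Section 9.4.3 never says that its classes use the best value. Under a best-value rule a patient is an increaser only if every reading is at least 50% above baseline, which is not the obvious reading of that class. This stands: a tilt towards responders can be claimed only for the best-value reading. The other readings still inflate error, so the missing visit matters either way.
- **Size.** The documents give no timing of AFP response. Section 1.4.1 leans towards early response, and 9.4.4 reads AFP decline at C2D1. With early response, error is close to nominal. This also stands, so the figures are ranges under assumptions. Section 1.2.3.1 gives only a responder share at best value (8 of 16), which does not settle timing.
- **Missing values.** Patients who leave before C2D1 may have no post-baseline AFP and fit none of the three classes. The end-of-treatment visit has a 60-day window (6.1.4), however, so some would have a value drawn. This is a minor point.
- **Importance.** This is one secondary association in about 19 patients, and 9.4.4 calls the sample too small to test TTP by pathway marker. That limits the weight of any result. It does not justify a method that can create a result when a better one uses the same data.

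**Conclusion.** The concern holds in conditional form. As written, 9.4.3 lets time on study influence AFP class and then compares TTP from first dose across those classes. With the best value and responses accruing over cycles, the comparison favours responders. With the last value or first 50% change, false positives rise without a consistent direction. With all responses present by C2D1, and patients lacking an on-therapy AFP left out, there is no material bias.

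For the planned three classes the assumed-model range is about 4–19% (best), 5–12% (last) and 14–41% (first 50% change). For an ever/never-responder split it is about 9–42% with gradual response and 5–6% with early response. All rest on n = 19, no true association and the dropout assumed above.

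A reader might infer that the planned test is bound to credit AFP decline with longer TTP, or that 42% or more is its error rate. The documents support neither. The direction depends on a choice that 9.4.3 leaves open, the higher figures belong to a two-group split that 9.4.3 does not state, and response timing is unknown. Nor does the point reach the primary endpoint, the sample size or the safety rule.

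**What to change.** In 9.4.3:

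1. Classify AFP change at C2D1, the visit already used in 9.4.4, among patients still on study and progression-free with an AFP value at that visit.
2. Run Kaplan-Meier and log-rank analyses from that landmark. Restricting to patients at risk removes the bias; moving the origin only changes how the curves read.
3. For Fisher's test, keep TTP of at least 6 months from first dose, the cut that 9.4.2 and 9.4.3 already report, in the same landmark patients.
4. Report how many patients have no landmark AFP.
5. Keep best AFP response as a descriptive proportion, and leave the baseline-AFP comparison unchanged.

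A Cox model with AFP response as a time-dependent covariate is an acceptable alternative.

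**Cost.** This changes wording only and uses data already collected. Patients who leave before C2D1, or lack a C2D1 AFP, drop out of this one analysis. Under the assumed dropout about 17–18 of 19 remain (16–18 if 30% of progressions are clinical and fall between scans). A C3D1 landmark would keep only about 10–11 at median 3 months and 13–14 at median 6 months.

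The number at C2D1 may be lower than assumed. Section 9.4.4 plans for 60% evaluable for AFP response on C2D1, at least 15 of at least 25 tissue cases, possibly pooled with phase I. It does not say whether the 60% already includes the baseline AFP restriction. Applied to this trial, that gives about 0.60 × 25 = 15 if it does and 0.60 × 19 = 11 if it does not.
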